4.2.4. Assessment Windows

4.2.4.1. Study Reporting Periods

Based on study design and variables under consideration, study time periods are defined as below.

Table 2: Definition of Study Reporting Periods

Analysis description	Analyzing Study Period	Start Date	End Date
General	Pre Treatment (Day -49 – Day 1/Week 24)	Date of informed consent	Prior to the date of first dose of vibegron on either study URO-901-3005 or URO-901-3006
	Treatment (Day 1/Week 24 – Week 52)	Date of first dose of vibegron on either study URO-901-3005 or URO-901-3006	Date of last dose of vibegron on URO-901-3006 + 5 or EOS, whichever is earlier
Adverse events	Prior (Summarized as Medical History)	Start date \geq date of informed consent on URO-901-3005 and $<$ date of first dose of vibegron in either study.	No restriction
	Treatment Emergent (TEAE)	Start date (AE begins or worsens in severity) \geq date of first dose of vibegron* and \leq date of last dose of vibegron + 5 days or EOS visit, whichever is earlier.	No restriction

Analysis description	Analyzing Study Period	Start Date	End Date
Prior or Concomitant Medication/ Procedure	Prior medication/ procedure	Start date < date of first vibegron dose	End date < date of first vibegron dose OR medication not marked as ‘ongoing’ on study URO-901-3005 and subject received placebo on study URO-901-3005
	Concomitant medication/ procedure	Start date \geq date of first dose of vibegron and \leq date of last vibegron dose + 5 days or EOS visit, whichever is earlier.	
		Start date < date of first vibegron dose, but ongoing during vibegron treatment period	End date \geq date of first vibegron dose OR medication marked as ‘ongoing’ on study URO-901-3005.

First and last dose of vibegron refer to the first and last dose across both study URO-901-3005 and URO-901-3006, for subjects who were treated with at least one dose of vibegron in study URO-901-3006.
 
EOS: End of study is defined as the date when the subject has completed one of the following: completes Week 52 Safety Follow-up, discontinued from the study, or is lost to follow-up.
 
*AEs with a start date equal to the date of first dose of vibegron will be considered treatment-emergent unless the relatedness to study drug is marked ‘Not applicable’.
 
Overlapping period: Medication start date \leq period start date < medication end date, medication start date < period end date \leq medication end date, or period start date \leq medication start or end date < period end date, then the medication is considered overlapping with the period.
			

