8.4. Adverse Events and Serious Adverse Events

The definitions of an AE or SAE can be found in Section 10.3.

AEs will be reported by the subject (or, when appropriate, by a caregiver, surrogate, or the subject's legally authorized representative).

The investigator and any qualified designees are responsible for detecting, documenting, and recording events that meet the definition of an AE or SAE and remain responsible for following up AEs that are serious, considered related to the study drug or study procedures, or that caused the subject to discontinue the study drug or the study (see Section 7).

8.4.1. Time Period and Frequency for Collecting Adverse Event and Serious Adverse Event Information

All AEs and SAEs will be collected from the signing of the informed consent form through the end of study. In addition, any AEs and SAEs reported within 21 days after the last dose of study drug (5 half-lives of vibegron [half-life approximately 80 hours]) will also be collected. AEs will be collected at the timepoints specified in the Schedule of Assessments (Section 1.3), and as observed or reported spontaneously by study subjects.

Medical occurrences that begin before the start of study drug, but after obtaining informed consent will be recorded in the AE section of the eCRF.

All SAEs (including serious AESIs) will be recorded and reported on the eCRF within **24 hours** of the study site personnel's knowledge of the event, as indicated in Section 8.4.4. Marking the event as "serious" will automatically send required notifications for Sponsor or designee review. The investigator will also submit any updated SAE data within 24 hours of receipt of the information. Nonserious AESIs will be reported on the eCRF within **72 hours** of the site's knowledge of the information

Investigators are not obligated to actively seek AE or SAE information after conclusion of the study participation. However, if the investigator learns of any SAE, including a death, at any time after a subject has been discharged from the study, and he/she considers the event to be reasonably related to the study drug or study participation, the investigator must promptly notify the Sponsor or designee.

The method of recording, evaluating, and assessing causality of AEs and SAEs and the procedures for completing and transmitting SAE reports are provided in Section 10.3.

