9.4.2. Safety Analyses

Safety analysis will be conducted using the SAF-Ext population and summarized by the Vibegron treatment group. The treatment-emergent period will be defined as the period of time from the first dose date of vibegron in this study through 21 days after the last dose of treatment, or the date of initiation of another investigational agent or surgical intervention, whichever occurs first. Safety will be assessed through summaries of adverse events, the frequency of treatment discontinuation due to adverse events, and clinical laboratory evaluations.

AEs will be coded using the latest version of MedDRA (20.0 or higher). The severity of all adverse events will be evaluated by the Investigator. The incidence of adverse events will be presented by system organ class and preferred term, relationship to study treatment and severity.

Laboratory data will consist of chemistry, hematology and urinalysis data. Only data collected by the central laboratory will be included in the analysis.

Descriptive statistics of observed values and change from baseline for vital signs and post void residual urine volume will be listed and summarized.

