7.3. Adverse Events

AEs will be coded using MedDRA version 23.0 or higher.

All reported AEs (whether treatment emergent or not) on both study URO-901-3005 and URO-901-3006 will be included in by-subject AE listings on the Safety Set Extension. Sorting will be by country, site, subject, date of event, SOC, PT and then verbatim description. An additional overall AE listing will be presented for subjects that were enrolled but not dosed with vibegron on URO-901-3006.

An AE will be considered treatment emergent (TEAE) if it begins or worsens in severity after the first dose of vibegron on study URO-901-3005 or URO-901-3006 through 5 days after the last dose of vibegron. Partial AE start dates will be imputed as detailed in [Section 4.2.3](#).

Summary tables will be based on TEAEs. The incidence of TEAEs will be presented using counts and percentages of subjects with TEAEs and tabulated by SOC and PT. SOC will be sorted in descending frequency and PT within SOC will be sorted by descending frequency based on the incidence across subjects overall. If a subject has multiple occurrences (start and stop) of an event associated with a specific SOC or PT within a SOC, a subject will only be counted once in the incidence count for the SOC or PT within SOC respectively.

An overall summary table of AEs will be presented detailing the number and percentage of subjects, and number of events for the following categories:

- At least one TEAE;

- At least one Treatment-Related TEAE;
- At least one Grade ≥ 3 TEAE (Mild = Grade 1, Moderate = Grade 2, Severe of Medically Significant = Grade 3, Life-Threatening = Grade 4, Death = Grade 5)
- At least one Grade ≥ 3 Treatment-Related TEAE;
- At least one Serious TEAE;
- At least one Serious Treatment-Related TEAE;
- At least one TEAE leading to Discontinuation from Study Medication;
- At least one TEAE of Special Interest;
- At least one Treatment-Related TEAE of Special Interest

Where not otherwise noted, all the following summaries are presented by PT:

- All TEAEs (by SOC and PT);
- Treatment-Related TEAEs (i.e., possibly or probably related);
- TEAEs occurring in 2% or more of the population;
- All TEAEs by SOC, PT, and maximum severity (where the maximum intensity per patient will be counted at each level of summarization);
- TEAEs with Grade ≥ 3 ;
- Treatment-Related TEAEs with Grade ≥ 3 ;
- Serious TEAEs;
- Treatment-Related Serious TEAEs;
- Fatal TEAEs;
- TEAEs leading to Discontinuation from Study Treatment;

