- TEAE of Special Interest (by protocol-defined AESI category);
- Treatment-Related TEAE of Special Interest (by protocol-defined AESI category);
- Non-fatal TEAEs;
- Hypertension TEAEs by Pre-existing Hypertension (Yes vs No) and Baseline Hypertension (Yes vs. No). Hypertension TEAEs will be selected as any TEAE with a preferred term of Hypertension.

In addition, a summary of all TEAEs by PT occurring in at least 2% of subjects will be created and ordered by descending overall frequency.

Adverse events of special interest for this study include:

- Adverse events consistent with urinary retention
- Adverse events suggestive of cystitis or urinary tract infection (UTI)
- Potential major cardiac and cerebrovascular events, including death (or any event with fatal outcome), myocardial infarction, cerebrovascular accident, hospitalization for unstable angina or chest pain, hospitalization for heart failure requiring hospitalization, and coronary revascularization/angioplasty/stent
- Adverse events consistent with hypertension (see protocol section 8.4.6)
- Adverse events consistent with orthostatic hypotension as confirmed by orthostatic vital signs
- Elevated serum aspartate aminotransferase (AST) or alanine aminotransferase (ALT) lab value requiring that study drug be temporarily withheld or permanently discontinued
- Neoplasms

Treatment listings will include the planned treatment duration, start and stop dates/times of the AE, study day (relative to start of double-blind treatment on URO-901-3005) and treatment day (relative to the day of first dose of vibegron). A treatment related AE is defined as an AE for which the investigator classifies the AE as being “Probably Related” or “Possibly Related” to study treatment on the Adverse Event CRF. Missing relationship and severity (intensity) will be imputed per Section 4.2.3.

The following additional listings will be provided:

- Listing of Deaths
- Listing of Serious TEAEs
- Listing of Treatment-Emergent AESIs
- Listing of TEAEs Leading to Withdrawal or Interruption of Study Treatment
- Listing of all AEs with a flag for TEAEs and onset (Prior = prior to first dose of vibegron or Treatment = on or after first dose of vibegron.)
- Listing of all medical history including pre-treatment adverse events with coded preferred terms in the hypertension AE search list:
 - Accelerated hypertension
 - Diastolic hypertension
 - Essential hypertension
 - Hypertension

- Hypertensive crisis
- Hypertensive emergency

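### The SAP closes the treatment-emergent AE window 5 days after the last dose, or sooner at EOS, against 21 days in the protocol, and does not declare the change

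*SAP*

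**What the plan says.** **Protocol.** Section 9.4.2 defines the treatment-emergent period as running from the "first dose date of vibegron in this study through 21 days after the last dose of treatment". It has one alternative end, "the date of initiation of another investigational agent or surgical intervention, whichever occurs first". Section 8.4.1 collects AEs through the end of study and, in addition, "any AEs and SAEs reported within 21 days after the last dose of study drug (5 half-lives of vibegron [half-life approximately 80 hours". Section 8.4.3 follows AEs to about 21 days after the last dose.

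**SAP.** The TEAE row of Table 2 (Section 4.2.4.1) closes the window at the "date of last dose of vibegron + 5 days or EOS visit, whichever is earlier". Section 7.3 defines the same flag as running "through 5 days after the last dose of vibegron" and does not mention EOS. The Table 2 footnote ties EOS to completing a Week 52 safety follow-up, to discontinuation or to loss to follow-up.

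**Use of the flag.** SAP 7.3 states: "Summary tables will be based on TEAEs". AEs that are not treatment-emergent appear only in listings, chiefly the "Listing of all AEs with a flag for TEAEs and onset".

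**Declared changes.** SAP Section 9 names four: the IPSS storage wording, added timepoints, COVID-19 and physical examination. None concerns the AE window, and the SAP gives no reason for 5 days.

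**The concern.** Safety is the primary objective, and AEs are the first endpoint listed under it. In a single-arm descriptive study the TEAE tables are the main AE result. A shorter post-dose window can only remove late AEs from those tables, so it makes the safety summary look somewhat more favourable. A reader with the protocol in hand would assume that 21 days had been applied.

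The protocol requires the late AEs to be collected and ties the collection period to the elimination of the drug. Five days is well short of that basis.

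Table 2 and Section 7.3 can also classify the same event differently, and the SAP does not say which governs. That defect would remain even if 5 days were justified.

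**Working it through.** **The protocol's own figure.** Inputs from Protocol 8.4.1: half-life about 80 h, 5 half-lives, 21 days.

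- 5 × 80 h = 400 h; 400 / 24 = 16.7 days. This is not exactly 21, but 21 days covers it (16.7 days rounded up to whole weeks is 3 weeks).
- 21 days = 504 h; 504 / 80 = 6.3 half-lives.
- 5 days = 120 h; 120 / 80 = 1.5 half-lives.

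Assuming simple first-order decline, the fraction of drug remaining is 0.5^(hours/80):

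- day 5: 0.5^1.5 = 35%
- day 16.7: 0.5^5 = 3.1%
- day 21: 0.5^6.3 = 1.3%

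**Days lost.**

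- SAP 7.3: 21 − 5 = 16 days; 16/21 = 76% of the post-dose period.
- Table 2 with the EOS visit on the day of the last dose: 21 − 0 = 21 days, the whole post-dose period.
- Against the whole window from first vibegron dose to last dose + 21 days: 16/(364 + 21) = 4.2% for 52 weeks of dosing and 16/(196 + 21) = 7.4% for 28 weeks.

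**How the three rules classify an AE**, for a man whose EOS visit falls on the day of his last dose and who has started no other agent or surgery:

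| Onset after last dose | Protocol 9.4.2 | SAP 7.3 | SAP Table 2 |
|---|---|---|---|
| Day 3 | TEAE | TEAE | not TEAE |
| Day 10 | TEAE | not TEAE | not TEAE |

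**When the EOS limit bites.** The schedule (Protocol 1.3) has no contact after Week 52/Early Withdrawal, Protocol 6.6 supplies no drug after that visit, and Protocol 4.4 treats the Week 52 visit as completion. For a completer dosed up to that visit, the Table 2 post-dose window is therefore about zero days. The Week 52 safety follow-up in the SAP footnote matches no scheduled visit. For early withdrawals the effect depends on when the withdrawal visit falls, which the documents do not fix.

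**Outputs affected (SAP Table 9).** Tables 14.3.2.1 to 14.3.2.16 (16 tables) and listings 14.3.2.18 to 14.3.2.20 (3 listings) use the flag. The Listing of Deaths (14.3.2.17) is not restricted to TEAEs. The table of TEAEs leading to discontinuation should hardly change, because those AEs start before dosing stops. The flag does not govern the laboratory, vital-sign, PVR and IPSS tables.

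**Scale, for illustration only.** Assume 300 men, 1:1 roll-over, no dropout and full observation after dosing.

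- Planned exposure: (150 × 52 + 150 × 28) × 7 / 365.25 = 230 person-years.
- Lost at 16 days each: 300 × 16 / 365.25 = 13.1 person-years; 13.1/230 = 5.7%.
- Lost at 21 days each: 300 × 21 / 365.25 = 17.2 person-years; 17.2/230 = 7.5%.

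These are not estimates of lost events. The documents give no AE rate, and capture after Week 52 is passive: "Investigators are not obligated to actively seek AE or SAE information after conclusion of the study participation".

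**The case against.** The strongest reply is that little depends on the flag. The study has no formal hypothesis, no safety test and no between-arm safety contrast. Late AEs stay in the all-AE listing with a TEAE flag, and deaths have their own listing. On size, 76% takes only the post-dose tail as its denominator. The person-years assume follow-up that the schedule does not provide, and 21 days per man for everyone, although the EOS argument is made for completers. With the planned 33% dropout there are about 200 completers, giving 200 × 21 / 365.25 = 11.5 person-years. EOS is also unclear: if the safety follow-up in the SAP footnote means the protocol's 21-day period, the limit need not cut below 5 days. Finally, Table 2 could be read as the formal rule and 7.3 as a short restatement of it.

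The points on size stand. The 76% should be read beside the 4.2% and 7.4%, and the person-years are illustrative. The loss for completers does depend on EOS being the Week 52 visit. The documents favour that reading: no later visit is scheduled, Protocol 1.3 calls the last visit of the parent study its end-of-study visit, and Protocol 8.4.1 adds the 21 days to collection through end of study.

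None of this removes the defect. Listings do not replace incidence tables for a primary-objective endpoint. The SAP gives no precedence between Table 2 and 7.3. The gap between 5 and 21 days exists under any reading of EOS. The protocol leaves statistical detail and the inclusion of parent-study data to the SAP, but that does not extend to replacing a stated 21 days without saying so.

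**Conclusion.** The concern holds and should be corrected before the TEAE flag is programmed. The SAP replaces the protocol's 21 days with 5 days in one place and with 5 days or EOS in another, and declares neither. The loss is 16 of 21 post-dose days under SAP 7.3. Under Table 2 it is up to all 21 for completers dosed to Week 52, if EOS is the Week 52 visit. The number of AEs affected cannot be derived and may be small, given passive capture. The half-life comparison rests on the protocol's 80 h and on first-order decline; the contradiction between the documents rests on no assumption.

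There are two lesser differences. The SAP omits the protocol's stop at another investigational agent or surgery, so its window could occasionally be the longer one. It also starts at the first vibegron dose in either study, which Protocol 9.1.1 and 9.3.2 anticipate although 9.4.2 is worded for this study only.

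**What to change.** Use one definition in SAP Table 2 and SAP 7.3: onset or worsening from the first vibegron dose in either study through last dose + 21 days. Remove the EOS limit for AEs.

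State in the SAP whether the protocol's cut-off at another investigational agent or surgical intervention applies. If it does, define surgical intervention and make clear that the cut-off does not remove AEs occurring while a man is still on drug. Record any remaining departure from Protocol 9.4.2 in SAP Section 9; a line noting the start date would be enough.

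If the sponsor prefers 5 days, it should declare and justify this in Section 9, remove the conflict between Table 2 and 7.3, and tabulate AEs with onset on days 6 to 21 separately.

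The same 5-day end appears in the general treatment row of Table 2 and in the concomitant procedure and medication definitions (SAP 5.5 and 5.6.2). These do not set the TEAE flag, but the SAP should say whether they are meant to differ from it.

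The cost is wording in two places, a Section 9 entry and one date rule. No new data are needed, since the protocol already requires these AEs to be collected. TEAE counts may rise slightly, and the added days will be less completely observed than on-study time, which the report should say.

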4.2.4.2. Analysis Visit Windows

Analysis visit windows for both diary and non-diary efficacy data are shown in Table 3. All observations will be given an analysis visit, assigned based on relative study day from the first blinded treatment in study URO-901-3005. If multiple repeats of the same assessment are observed within an analysis window, unless the measure was intended to be averaged over replicates, the record closest to the nominal time (earlier in case of a tie) will be used for by-visit summaries. If fewer than three of the diary days are within the analysis window, only the data within the window will be used to calculate visit-level averages.

Table 3: Efficacy Analysis Visit Window Slotting

Analysis window label	Non-diary data			Diary data		
	Nominal visit	Nominal day	Visit Window	Nominal visit ^a	Nominal day	Window
Baseline	Visit 3	1	NA ^b	Run-in	-1	[-7 ^c , -1]
Week 1	Visit 4	8	[2, 11]			
Week 2	Visit 5	15	[12, 22]	Visit 4	15	[7,18]
Week 4	Visit 6	29	[23, 42]	Visit 5	29	[19, 39]
Week 8	Visit 7	57	[43, 70]	Visit 6	57	[47, 67]
Week 12	Visit 8	85	[71, 98]	Visit 7	85	[68, 102]
Week 16	Visit 9	113	[99, 126]	Visit 8	113	[103, 123]
Week 20	Visit 10	141	[127, 154]	Visit 9	141	[131, 151]
Week 24	Visit 11	169	[155, 182 ^b]	Visit 10	169	[159, 179]
Week 28	Visit 12	197	[183 ^d , 224]	Visit 11	197	[187, 207]
Week 36	Visit 13	253	[225, 308]	Visit 12	253	[243, 263]
Week 52	Visit 14	365	> Day 309	Visit 13	365	[345, 385]

a Nominal visit for diary data is the visit where the diary was dispensed.

b Must have occurred prior to the first dose administered in study URO-901-3006.

c If randomization was delayed for any reason, diaries completed within 7 days prior to the baseline visit will still be considered within the analysis window.

d Must have occurred on or after the first dose administered in study URO-901-3006.

For all non-diary safety data including safety laboratory, vital signs, and PVR volume to be summarized by visit, data records will be slotted to one of the protocol-specified visits using the following algorithm:

1. Determine relative study day and last dose day:

Relative study day will be derived as described in Section 4.3.3.

Note that the date of first double-blind dose on URO-901-3005 is Day 1 and the day before the date of double-blind first dose is Day -1. There is no Study Day 0.

2. For non-early withdrawal records, if a nominal visit number for a scheduled visit was assigned, then it will be used to summarize the record after checking to make sure that visit numbers match with therapy phases:

- Check that all records entered as a pre-treatment visit for study URO-901-3005 occur on or before the day of the first dose of double-blind treatment (i.e. day ≤1). Any record with day > 1 should be re-slotted to an on-treatment visit using the relative day window below.
- Check that all records slotted to an on-treatment visit for study URO-901-3005 and all records for study URO-901-3006 are on or after the day of the first dose of double-blind treatment. If they are not, the visit should be moved to pre-treatment.

3. Any early withdrawal record (regardless of the visit number assigned), any unscheduled visit record at any time, any repeat visit record, or any record for which the visit number was missing or the visit number was not for a scheduled visit, should be slotted or re-slotted to a visit using the window below.

Table 4: Analysis Visit Window Slotting

Analysis window label	URO-901-3005 Randomized Arm					
	Vibegron			Placebo		
	Nominal visit	Nominal day	Visit Window	Nominal visit	Nominal day	Visit Window
Baseline	Visit 3	1	NA ^a	Visit 3	1	[1,182 ^b]
Week 1	Visit 4	8	[2, 11]	NA	NA	NA
Week 2	Visit 5	15	[12, 22]	NA	NA	NA
Week 4	Visit 6	29	[23, 42]	Visit 12	197	[183 ^c ,224]
Week 8	Visit 7	57	[43, 70]	NA	NA	NA
Week 12	Visit 8	85	[71, 98]	Visit 13	253	[225,308]
Week 16	Visit 9	113	[99, 126]	NA	NA	NA
Week 20	Visit 10	141	[127, 154]	NA	NA	NA
Week 24	Visit 11	169	[155, 182 ^a]	NA	NA	NA
Week 28	Visit 12	197	[183 ^b , 224]	Visit 14	365	> Day 309
Week 36	Visit 13	253	[225, 308]	NA	NA	NA
Week 52	Visit 14	365	> Day 309	NA	NA	NA

a Must have occurred prior to the first dose administered in study URO-901-3005.

b Must have occurred prior to the date of first dose administered in study URO-901-3006.

c Must have occurred on or after the date of first dose administered in study URO-901-3006.

Note: The cut-off days to define the window for slotting through Week 20 are aligned with study URO-901-3005.

For parameters which were **not** scheduled to be collected at all visits, the all-inclusive visit intervals defined for all visits (i.e., the window defined above) will still be used to slot records. If a value is slotted to a visit unscheduled for a parameter, it will not be summarized (and not be included in the efficacy datasets) but will be included in data listings.

4. If after all records have been slotted or re-slotted, there are multiple valid records within a visit, use the record following the rules below:
 - If there are multiple values for an endpoint in one window, the visit closest to the nominal day will be selected for by-visit displays. If the visits are equidistant from the nominal day, then the earlier visit will be selected. All values will be stored in analysis datasets.

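### SAP Table 4 puts unworkable footnotes on the vibegron-arm Week 24 and Week 28 windows, and its placebo-arm Baseline row exposes an unresolved conflict over the safety baseline

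*SAP*

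**What the plan says.** SAP Section 4.2.4.2 sets out four steps for placing non-diary safety records (laboratory, vital signs, PVR) at visits.

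- **Origin of study days (step 1).** "Note that the date of first double-blind dose on URO-901-3005 is Day 1".
- **Scheduled visits (step 2).** Records that are not early-withdrawal records and have a scheduled visit number keep that visit, after a check that it fits the treatment phase.
- **Records that depend on Table 4 (step 3).** "Any early withdrawal record (regardless of the visit number assigned), any unscheduled visit record at any time, any repeat visit record", and records whose visit number is missing or not a scheduled one.
- **Several records in one window (step 4).** "the visit closest to the nominal day will be selected for by-visit displays".

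Table 4 defines three footnotes. Footnote a looks back to the parent study: "Must have occurred prior to the first dose administered in study URO-901-3005". Footnote b takes the start of extension dosing as its reference and admits only what came earlier: "Must have occurred prior to the date of first dose administered in study URO-901-3006". Footnote c is the complement of b, admitting only records from the start of extension dosing onward.

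In the vibegron column, a stands on the Day 182 limit of Week 24 and b on the Day 183 limit of Week 28. In the placebo column, b stands on Day 182 (Baseline) and c on Day 183 (Week 4). Table 3, for non-diary efficacy data, has on Day 182 the condition "Must have occurred prior to the first dose administered in study URO-901-3006" and on Day 183 the condition "Must have occurred on or after the first dose administered in study URO-901-3006".

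The placebo-arm Baseline row of Table 4 reads Visit 3, nominal Day 1, window Days 1 to 182. In both arms the second-to-last window in use ends at Day 308, and the last takes days greater than 309.

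**The concern.** The vibegron-arm conditions contradict the day ranges they qualify. Week 24 starts on Day 155 but must precede Day 1. Week 28 should hold the first on-drug extension data but must precede the first extension dose. A program that applies the footnotes as printed would place no step 3 record in either window.

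PVR and vital signs are primary-objective endpoints (SAP Section 1.1.1), and both are scheduled at Week 28. Protocol Section 7.1 sends men who stop study drug, including those with a PVR of 300 mL or more or an AE of urinary retention, to the Early Withdrawal assessments. Some records affected are therefore the ones this safety study most wants to tabulate. For PVR, SAP Section 7.7 names by-visit summaries, categories and a listing, but no maximum or last-value summary.

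The placebo-arm Baseline row raises a wider question: whether change from baseline in the 28-week group starts from Day 1 of the parent study or from the last value before vibegron, normally about Week 24.

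**Working it through.** **1. Timing inputs.** Visit 11 is Day 169 ± 4, so Day 165 to 173 (Protocol Section 10.7.1). Entry to the extension follows within 7 days (Protocol Section 5). Assuming that dosing starts at entry, the first extension dose falls between Day 165 + 0 = 165 and Day 173 + 7 = 180.

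**2. Days in each vibegron-arm window that meet the footnote.**

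| Window | Days | As printed | With Week 24 = b, Week 28 = c |
|---|---|---|---|
| Week 24, 155 to 182 | 28 | a (day < 1): 0 | 10 (dose on Day 165) to 25 (dose on Day 180) |
| Week 28, 183 to 224 | 42 | b (day < first extension dose): 0 | 42 |

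The Week 24 zero holds for every subject. The Week 28 zero holds on the protocol schedule. That window opens only if the first extension dose is on Day 184 or later: 1 day for a dose on Day 184, 7 for Day 190, 14 for Day 197. SAP Section 9.3 says visit windows were widened during COVID-19 without giving the amount, so late entry is possible. Even then, only records before the extension dose would be admitted, the reverse of the Table 3 condition.

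**3. What relettering leaves open.** With b and c in place, 28 − 25 = 3 to 28 − 10 = 18 days, from the first extension dose to Day 182, belong to neither window. Week 24 requires a pre-dose record and Week 28 starts at Day 183. The placebo column has the same gap between Baseline and Week 4. Day 309 also falls in no window, because one ends at 308 and the next starts above 309.

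**4. Men affected at Week 28.** The plan expects 100 one-year completers at about 33% dropout (Protocol Section 9.7, SAP Section 1.2.4). Taking half of 300, 150 × (1 − 0.33) = 100.5, which reproduces that figure and supports 150 men on the 52-week course. The extension lasts 28 × 7 = 196 days. Uniform dropout over it is my assumption.

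A man who leaves after Visit 12 already has a scheduled Week 28 record, kept by step 2. Only men leaving from Day 183 up to the day before Visit 12 can lose their sole Week 28 value:

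- Visit 12 on Day 197 (Days 183 to 196, 14 days): 150 × 0.33 × 14/196 = 3.5
- Visit 12 on Day 193 (10 days): 150 × 0.33 × 10/196 = 2.5
- Visit 12 on Day 201 (18 days): 150 × 0.33 × 18/196 = 4.5

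Men leaving in the step 3 gap are not counted, because relettering alone would not place their records either.

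**5. Placebo-arm Baseline.** Under the closest-to-nominal rule, a Day 1 record lies 0 days from nominal and a Day 169 record lies 168 days away, so Day 1 is chosen. The documents give two definitions:

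| Source | Safety baseline |
|---|---|
| SAP Section 1.1 | most recent assessment before starting vibegron |
| SAP Section 3.1.2 | last observation before the first vibegron dose |
| SAP Section 4.3.4 | last value before the first double-blind dose |
| Protocol Section 9.3.2 | the parent-study baseline |

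For men randomized to vibegron the definitions coincide. For men randomized to placebo they differ by about 24 weeks. SAP Section 9 does not list a change of safety baseline from the protocol.

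**The case against.** The strongest reply is that this is a lettering slip with recoverable intent. The marker order in Table 3 (b on Baseline and Week 24, d on Week 28) recurs in the vibegron column of Table 4 as a, a, b. That would fit a copied table in which the letters were not updated. The placebo column is right on the same limits, the day ranges do not overlap, and the SAP describes its windows as all-inclusive. No inferential safety testing is planned. All of this stands, and it limits the point to a correctable specification error. It does not remove the error: the footnotes are operative conditions, and Table 3 is not a fully clean guide, since its own Baseline row carries the pre-extension-dose footnote.

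A reader might infer three stronger things that the documents do not support.

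- **About 11 men lose PVR, laboratory and blood pressure data.** Counting all 42 days gives 150 × 0.33 × 42/196 = 10.6, but most of those men would already have a scheduled Week 28 record. Laboratory tests are not scheduled at Week 28 (Protocol Section 1.3), and the SAP does not summarise values slotted to a visit unscheduled for that parameter.
- **The records are lost.** Listings, any-time on-treatment endpoints, laboratory shifts to maximum, minimum and last value, maximum and end-of-treatment vital-sign changes, and AE tables do not use these footnotes. At Week 24 the effect is small, because the safety set requires completion of the parent treatment period and Visit 11 keeps its nominal visit.
- **The placebo Baseline row is simply wrong.** Nominal Day 1 agrees with SAP Section 4.3.4 and Protocol Section 9.3.2. The closest-to-nominal rule concerns by-visit displays and would not override an explicit baseline definition. The fault is that two definitions stand side by side.

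**Conclusion.** The point holds as a specification error that should be corrected. As printed, the vibegron-arm Week 24 window of Table 4 admits no step 3 record, and the Week 28 window admits none on the protocol schedule. That the markers slipped by one letter is an inference from Table 3 and the placebo column.

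The direct effect is confined to by-visit PVR and vital-sign displays. About 3.5 men (2.5 to 4.5, depending on the Visit 12 day) would lose their only Week 28 value. This rests on 150 men, 33% dropout, uniform timing and a literal reading of the footnotes. The count scales in proportion to the withdrawal rate in those days.

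The baseline conflict has the wider reach. It can change every change-from-baseline safety summary in the 28-week group, about 300 − 150 = 150 men on the same split. The documents give no data from which to size the shift.

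**What to change.** 1. In the vibegron column of Table 4, give Week 24 footnote b and Week 28 footnote c.
2. Make the boundary between Week 24 and Week 28 the date of the first URO-901-3006 dose, so that records after that dose but on or before Day 182 go to Week 28. Treat the Baseline/Week 4 boundary in the placebo column the same way.
3. Assign Day 309 to a window, in Table 3 as well as Table 4.
4. State one safety baseline and align SAP Sections 1.1, 3.1.2 and 4.3.4 and the placebo-arm Baseline row with it. If the last value before vibegron is kept, define that row as the last record before the first URO-901-3006 dose, and list the departure from Protocol Section 9.3.2 in SAP Section 9.

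The cost is text edits to the SAP and matching programming specifications before database lock. No new data and no change to study conduct are needed.
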